2. STUDY SYNOPSIS

The aim of this study is to address the question: Does early treatment of index case and early pre/post exposure prophylaxis of household members with intranasal heparin reduce transmission to household family contacts on Severe acute respiratory syndrome Coronavirus 2 (SARS-CoV-2) Polymerase chain reaction (PCR) assay by day 10, and subsequently reduce the burden of severe Coronavirus disease 2019 (COVID-19) as

measured by hospitalisation rates in exposed/infected people? A secondary outcome is whether intranasal heparin reduces the duration of transmissibility within the index case.

Multi-centre, prospective, cluster randomised, placebo-controlled two-arm superiority clinical trial.

Individual households with at least one person with PCR or RAT confirmed SARS-CoV-2 infection will be randomised so that all consenting people in that household receive intranasal heparin or placebo. Participants will receive intervention for 10 days and undergo 12 months of follow-up. The primary outcomes are achieved within 10 days. The majority of secondary outcomes related to primary COVID-19 infection are followed for 28 days from randomisation. The secondary outcomes related to "long COVID" are monitored at 6 and 12 months post randomisation.

The target sample size for the primary outcome is 1100 individuals. We planned to enroll 268 households and 1072 individuals.

The rate of subsequent PCR confirmed SARS-CoV-2 infections in exposed households will be measured to determine the effect of intranasal heparin on reducing transmission to close contacts.

The rate of symptom development in all participants will be used to determine effect of treatment in preventing symptomatic disease. The rate of hospitalisation of all participants will be measured to determine the effect of treatment on development of severe disease. The presence of clinical neurological long COVID symptoms will be assessed at 6 and 12 months to determine the effect of treatment on long COVID.

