3.7. Handling of missing data

If less than 10% of data is missing, the primary analysis will be conducted using the participants with available data for each outcome. However, if there are >10% missing data in the primary or secondary outcomes, we will conduct the analysis under a plausible assumption regarding the missingness mechanism that will be guided using expert clinical knowledge prior to observing the data, which will be determined by generating directed acyclic graphs. We suspect that the data will be recoverable (that is able to be estimated without bias from the observed data alone), and multiple imputation will be used to handle the missing data in all

outcomes. Imputations will be generated using chained equations, also known as fully conditional specification, with 50 imputed datasets and 10 iterations between each imputation. Ideally this would be conducted using a single regression model for all outcomes, although it may be necessary to impute incomplete outcomes using separate models. Imputation will be carried out separately by arm, to ensure that any treatment effects are maintained. Baseline characteristics as well as any variables that are predictors of missingness and/or associated with the incomplete outcomes will be included as auxiliary variables in the imputation model. Estimates of interest will be obtained using Rubin's rules, and will be reported with 95% confidence intervals and *p*-values.

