The analysis will follow the intention to treat principle, but only some households will be eligible for this objective. A household will be eligible if there is at least one participant in the household who tested positive to SARS-CoV-2 by PCR on Day 1 and one participant who tested negative to SARS-CoV-2 by PCR on Day 1, using the health care provider collected swab. It does not matter whether it was the index case or another household member who tested positive. Households where all participants test positive or where all participants test negative will not be eligible for this analysis.

Treatment arms will be compared using generalised linear mixed models (GLM) with infection status as the binary outcome, adjusting for stratification factors (time from positive test to randomisation, whether the index case is a child < 5 years), participant age, inhaled steroid use at baseline, days since symptom onset at randomisation, whether there are children in the household and household size (referred to as the defined baseline covariate set, see Section 3.9), with household as random effect to take the clustering by household into account. Both relative and absolute differences in proportions will be reported with 95% confidence intervals.

Relative differences (risk ratios) between the treatment arms will be calculated using a Poisson regression with robust standard errors in Stata as follows:

xtpoisson outcome i.arm baseline_covariates, re vce(robust) irr

Absolute differences (risk difference) between the treatment arms will be calculated in Stata as follows using a mixed effects GLM with random intercepts: megIm outcome i.arm baseline_covariates || household:, family(bin) link(logit)

The margins statement will be used to compute the risk difference by subtracting the probability of the outcome in the control arm from the probability in the treatment arm margins i.arm, atmeans post lincom _b[1.arm] - _b[0.arm]

Both these models are fairly complicated models to fit and might not converge if sparse data is encountered, given all the baseline covariates included. If the models do not converge, the following strategies will be tried:

- Exclude some of the baseline covariates especially binary covariates, covariates with sparse categories, or covariates with little variability
- Or, fit the following simpler models

Relative differences (risk ratios) between the treatment arms will be calculated in Stata as follows using robust standard errors:

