glm outcome i.arm baseline_covariates, fam(bin) link(log) nolog eform vce(cluster household)

Absolute differences (risk difference) between the treatment arms will be calculated in Stata as follows using robust standard errors:

glm outcome i.arm baseline_covariates, fam(bin) link(identity) nolog vce(cluster household)

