6.4 Secondary outcome 4. Impact on peak severity of illness

Measure 4.1

Number of household members swab positive on day 1 by PCR, hospitalised with COVID-19 by day 28 from randomisation

Estimand

Population: Household members who test positive for SARS CoV-2 on day 1 by PCR

Statistical Analysis Plan

Treatment: Initially randomised intervention to unfractionated intranasal heparin 1400u each nostril (as heparin solution 5,000u/ml, 140microL/actuation, TWO actuations each nostril) THREE times daily via a plastic nasal inhalator device or saline control and any subsequent deviations to the per protocol use of the intervention over 10 days

Outcome: Participants reported being hospitalised in first 28 days

Summary measure: Both relative (risk ratio) and absolute differences (risk difference) in proportions will be reported with 95% confidence intervals

Potential intercurrent events:

Index case in the household not taking study drug. This is defined as compliance <90% Participant (this household member) not taking study drug. This is defined as compliance <90% Either participant (this household member) or index case stop treatment due to adverse event Participant received an anti-viral

Strategy for handling intercurrent event:

All intercurrent events will be handled through the treatment policy strategy, which means that the intercurrent events will be ignored.

The same analysis as described in Section 5.1 for the primary analysis will be done.

Measure 4.2

Number of household contacts swab negative on day 1 by PCR, hospitalised with COVID-19 by day 28 from randomisation

Estimand

Population: Household contacts who test negative for SARS CoV-2 on day 1 by PCR

Treatment: Initially randomised intervention to unfractionated intranasal heparin 1400u each nostril (as heparin solution 5,000u/ml, 140microL/actuation, TWO actuations each nostril) THREE times daily via a plastic nasal inhalator device or saline control and any subsequent deviations to the per protocol use of the intervention over 10 days

Outcome: Participants reported being hospitalised in first 28 days

Summary measure: Both relative (risk ratio) and absolute differences (risk difference) in proportions will be reported with 95% confidence intervals

Potential intercurrent events:

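### Measures 4.1 and 4.2 have no rule for zero or few hospitalisations, so an empty arm against 1 to 5 events gives a risk-ratio interval that wrongly excludes 1

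*SAP*

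**What the plan says.** Section 6.4 defines two hospitalisation measures: 4.1 for participants PCR positive on day 1, and 4.2 for household contacts PCR negative on day 1. For both, the outcome line reads "Outcome: Participants reported being hospitalised in first 28 days" and the summary measure is "Both relative (risk ratio) and absolute differences (risk difference) in proportions will be reported with 95% confidence intervals". For the method, both say "The same analysis as described in Section 5.1 for the primary analysis will be done".

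Section 5.1 takes the risk ratio from "xtpoisson outcome i.arm baseline_covariates, re vce(robust) irr". If that does not converge, the simpler option is "glm outcome i.arm baseline_covariates, fam(bin) link(log) nolog eform vce(cluster household" with the closing bracket. The risk difference comes from a mixed logit model through marginal predictions, or from an identity-link GLM as the simpler option.

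Section 5.1 discusses sparse data only as a threat to convergence: "Both these models are fairly complicated models to fit and might not converge if sparse data is encountered". The remedies there and in Section 3.9 are to drop covariates or move to the simpler GLM. Nowhere does the SAP give an expected hospitalisation rate, a minimum number of events, or a rule for an arm with none.

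**The concern.** The Section 5.1 models suit an outcome that most contacts were expected to have (Section 2.6 plans on 85% and 75%). Hospitalisation among community participants may be far less frequent, and its events are split between two analysis sets. With an empty arm the maximum-likelihood log risk ratio is minus infinity. The software stops at some large finite value. A model-based standard error would then be huge and warn the reader, but a robust one stays small. The plan would print a tight interval far from 1, in favour of heparin or against it, on as few as one event. Hospitalisation is part of the aim stated in the synopsis, so such an interval could be quoted as a finding.

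**Working it through.** **Inputs.** The SAP has no figure for hospitalisation to reproduce. Group sizes are therefore borrowed from Section 2.6: 134 households per arm and 3 contacts per household. That plan checks out. About 250 per arm for 85% vs 75% (two-sided 5%, 80% power), times 1 + (3 − 1) × 0.2 = 1.4, gives 350 contacts, or 117 households, against the stated 360 and 120. Then 120/0.9 = 133.3, rounded up to 134. Two illustrative sizes follow: 134 per arm (one person per household, as for 4.1) and 134 × 3 = 402 per arm (as for 4.2). The true day 1 split is not stated.

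**Why the standard error stays small.** Let one arm have no events. Let the other have k events in k different households, with H equal-sized households per arm and no covariates. The household-clustered sandwich variance of the log risk ratio is the sum of two parts:
- arm with k events: 1/k − 1/H
- empty arm: every residual is minus its fitted mean, so the squared sum over the squared total is 1/H, however small the fitted mean becomes

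The sum is 1/k, so SE = 1/√k. The empty arm, which carries no information on the log scale, adds almost nothing. The interval excludes 1 once the fitted log risk ratio falls below −1.96/√k, which is −1.96 for k = 1. The iterations go far past that.

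**Numerical check** (heparin 0 events, control k):

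| k | robust SE | log RR, gradient tolerance 1e-5 | log RR, second program | Fisher p (134 per arm) | Fisher p (402 per arm) |
|---|---|---|---|---|---|
| 1 | 1.00 | −11.7 | −20.4 | 1.00 | 1.00 |
| 2 | 0.71 | −12.7 | −20.4 | 0.50 | 0.50 |
| 3 | 0.58 | −12.7 | −21.4 | 0.25 | 0.25 |
| 4 | 0.50 | not run | −21.4 | 0.12 | 0.12 |
| 5 | 0.45 | −13.7 | −21.4 | 0.06 | 0.06 |
| 6 | 0.41 | not run | −22.4 | 0.03 | 0.03 |

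The third column is a gamma random-effects Poisson, the likelihood behind the specified command. The fourth is a Poisson GLM with household-clustered SE. All fits converged. For k = 1 the third column gives RR = exp(−11.69) = 8e-6, with interval 8e-6 × exp(±1.96 × 1.00), or 1e-6 to 6e-5. The two programs differ in the size of the RR and agree on the SE. The model-based SE in the random-effects fits was about 330 to 470, so the narrow interval comes from the sandwich alone. The log-binomial fallback gave robust SE 1.00, 0.58 and 0.45 for k = 1, 3 and 5, with log RR −12 to −14. By contrast, 1 vs 3 events at 402 per arm gives RR 0.33 with interval 0.03 to 3.2.

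The exact conditional upper 95% limit for the RR, with u = 1 − 0.025^(1/k) and limit u/(1 − u), is 39, 5.3, 2.4, 1.5 and 1.09 for k = 1 to 5, and 0.85 for k = 6.

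**How often.** With the same risk r in both arms and independence, q = (1 − r)^N is the chance that an arm is empty, and 2q(1 − q) is the chance that exactly one is. The chance of 0 vs 1 to 5 is 2q[P(X ≤ 5) − q], X binomial(N, r).

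| Assumed risk | 134 per arm: one empty | of which 0 vs 1–5 | 402 per arm: one empty | of which 0 vs 1–5 |
|---|---|---|---|---|
| 0.25% | 40.8% | 40.8% | 46.4% | 46.3% |
| 0.5% | 50.0% | 50.0% | 23.1% | 22.7% |
| 1% | 38.5% | 38.4% | 3.5% | 2.7% |
| 2% | 12.5% | 11.7% | 0.1% | 0.01% |
| 5% | 0.2% | 0.07% | under 0.1% | under 0.1% |

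**The case against.** Several points on the other side stand.
- Rarity is an assumption. The problem is negligible at 5% with 134 per arm and at 2% with 402. The outcome line, read literally, counts any hospitalisation, which would raise the rate.
- Table 15 plans N (%) by arm and the risk difference beside the risk ratio, and has no p-value column. A reader who sees 0 against 2 can discount the ratio, and the misleading output is an interval rather than a planned p-value.
- The risk difference stays finite. For 0 vs 3 of 402 it is −0.75% (−1.6% to +0.1%). Its Wald interval does exclude 0 from 0 vs 4, where Fisher's p is 0.12.
- Stata was not run. The full baseline covariate set was not fitted either, although fits with added covariates converged with the same result. If the full model failed, the planned response would be fewer covariates or the log-binomial model. Both keep the arm term, which is the cause.

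A reader might also infer more than the SAP supports.
- That every empty arm gives false significance. At 0 vs 0 there is no estimate, and from 0 vs 6 an exact test is also below 0.05, though the printed RR and its interval still mean nothing.
- That the mixed logit model breaks the risk difference. The SAP reports a difference of predicted probabilities, which stays finite when the arm coefficient diverges.
- That "Imputation will be carried out separately by arm, to ensure that any treatment effects are maintained" makes the analysis impossible. Imputation applies only above 10% missing data, and no calculation shows a failure.
- That a promised pooled analysis was left out. The synopsis says "The rate of hospitalisation of all participants will be measured to determine the effect of treatment on development of severe disease", and 4.1 and 4.2 together cover essentially everyone with a day 1 result. Pooling is a preference, and its absence is no error.

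**Conclusion.** The gap is real and limited to the risk ratio in two secondary measures. With 0 against 1 to 5 events, Section 5.1 as written gives a risk ratio whose size is set by the stopping tolerance and an interval of about ±1.96/√k on the log scale that wrongly excludes 1. The convergence remedies neither detect this nor cure it. How likely it is depends on a rate that the SAP does not give. With 134 per arm it is a serious risk at hospitalisation risks up to about 2%, and with 402 per arm up to about 0.5%. These chances assume equal risks, independence and the planned number of households. The primary analysis is unaffected, so this should be fixed but does not put the trial's main result in doubt.

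**What to change.** In Section 6.4, replace the bare reference to Section 5.1 for Measures 4.1 and 4.2 with a rule fixed before the arms are compared:
- Always report n/N (%) by arm, as Table 15 already plans.
- If either arm has fewer than a stated minimum of events (for example 5), report no model-based risk ratio. Give instead a permutation or exact test at household level (any hospitalisation in the household, arm permuted within randomisation strata), with an exact or score-type household-level interval for the risk difference.
- Otherwise use the Section 5.1 models.

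The cost is a few sentences, a footnote to Table 15 and a short piece of code, with no new data. When events are few, the result is not adjusted for covariates and refers to households rather than participants. The threshold of 5 is a convention, and any value fixed in advance that rules out an empty arm removes the fault described here.

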2.2. Secondary objectives

1. To test the efficacy of intranasal heparin to reduce SARS-CoV-2 viral shedding over 10 days from day of positive swab (health professional collected swab day 3 and 5, and day 10)

Measure:

- 1.1. Total number of index cases and household contacts combined (nasopharyngeal swab positive on day 1), who remain swab positive on day 3
- 1.2. Total number of index cases and household contacts combined (nasopharyngeal swab positive on day 1), who remain swab positive on day 5
- 1.3. Total number of index cases and household contacts combined (nasopharyngeal swab positive on day 1), who remain swab positive on day 10
- 1.4. Time to swab negative based on health care provider collected nasal swab for household members (index cases and household contacts) who were swab positive on day 1 by PCR
- 1.5. Mean Ct values on days 3, 5 and 10
- 1.6. Lowest Ct value amongst household members who become positive during the first 10 days
- 2. To test the safety of intranasal heparin for treatment of adult and child outpatients with SARS-CoV-2 infection.

Measure:

2.1 The number of participants who discontinue treatment prior to day 10 from randomisation as a measure of treatment tolerability

2.2: Listing of adverse events and serious adverse events

3. To test whether intranasal heparin administration reduces symptomatic disease in index cases and household contacts.

Measure:

3.1 Number of household contacts (swab negative on day 1 of study) becoming symptomatic of COVID-19 in the next 28 days

Symptomatic COVID-19 is defined as:

- Fever or chills PLUS ≥1 respiratory symptom (sore throat, cough, shortness of breath);
- OR 2 respiratory symptoms (sore throat, cough, shortness of breath);
- OR 1 respiratory symptom (sore throat, cough, shortness of breath) PLUS ≥2 non-respiratory symptoms (chills, nausea, vomiting, diarrhea, headache, conjunctivitis, myalgia, arthralgia, loss of taste or smell, fatigue or general malaise).

3.2 Time to symptom resolution for index case and household contacts who were SARS-CoV-2 positive on day 1, during the study period as measured with daily symptom diary until day 28

- Common symptoms included in the symptom diary:
- Fever or chills
- Cough
- Shortness of breath or difficulty breathing
- Fatigue
- Muscle or body aches
- Headache
- New loss of taste or smell
- Sore throat
- Congestion or runny nose
- Nausea or vomiting
- Diarrheoa
- 4. To test the impact of intranasal heparin on peak severity of illness.

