Measure:

- 4.1. Number of index cases and household contacts swab positive on day 1, hospitalised with COVID-19 by day 28 from randomisation
- 4.2. Number of household contacts swab negative on day 1, hospitalised with COVID-19 by day 28 from randomisation
- 4.3 Maximum severity score of participants (index case and household contacts swab positive) during the study period as recorded by daily symptom diary up to day 28.

A COVID-19 Composite Subjective Symptom Severity Score (CCSSSS) will be generated using the 11 common symptoms for COVID-19 infection listed at the Centers for Disease Control and Prevention (CDC) website and a self-rated symptom severity assessment generated for each symptom on a daily basis using a Likert scale for each symptom (Scale 0-3: not present, mild, moderate, severe).

Common symptoms:

- Fever or chills
- Cough
- Shortness of breath or difficulty breathing
- Fatigue
- Muscle or body aches
- Headache
- New loss of taste or smell
- Sore throat
- Congestion or runny nose
- Nausea or vomiting

• Diarrhea

Each symptom will be assigned a score of 0 if not present, 1 if mild, 2 if moderate and 3 if severe. These scores for each symptom will be added together to get the CCSSSS for each day.

5. To assess the impact of intranasal heparin on long COVID neurological symptoms.

Measure:

5.1 Number of participants with clinical symptoms of neurological long COVID at 6 months post randomisation.

The following symptoms were rated via telehealth or in person using a self-rated symptom assessment using a Likert scale (0-3: absent, mild, moderate, severe) for each symptom:

- Fatigue
- Malaise
- Daytime tiredness
- Impaired concentration
- Brain fog
- Sleep disturbance
- Forgetfulness
- Confusion
- Headache
- Dizziness
- Nausea
- Hypo/anosmia
- Hypo/ageusia
- Impaired walking
- Tingling feet or hands
- Burning feet or hands
- Numb feet or hands
- Impaired fine motor skills
- Muscle pain
- Epilepsy
- Anxiety
- Depression

For participants over 16 years of age, cognition and mood were assessed using the harmonised procedures developed by the Neuro-COVID Neuropsychology International Task force. Included measures were:

- Cognitive screening using Telephone Montreal Cognitive Assessment (T-MoCA)
- Subjective cognitive complaints using Patient's Assessment of Own Functioning Inventory (PAOFI)
- Attention/working memory using the Wechsler Adult Intelligence Scale (WAIS) digit span
- Mood using the Depression, Anxiety and Stress Scales (DASS)

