Index case in the household not taking study drug. This is defined as compliance <90% Participant (this household member) not taking study drug. This is defined as compliance <90% Either participant (this household member) or index case stop treatment due to adverse event Participant received an anti-viral

Strategy for handling intercurrent event:

All intercurrent events will be handled through the treatment policy strategy, which means that the intercurrent events will be ignored.

The same analysis as described in Section 5.1 for the primary analysis will be done.

Measure 4.3

Maximum severity score of participants (household members swab positive) during the study period as recorded by daily symptom diary up to day 28.

A CCSSSS will be calculated using the 11 common symptoms for COVID-19 infection listed at the CDC website (fever or chills, cough, shortness of breath or difficulty breathing, fatigue, muscle or body aches, headache, new loss of taste or smell, sore throat, congestion or runny nose, nausea or vomiting, diarrhea) and a self-rated symptom severity assessment generated for each symptom on a daily basis using a Likert scale for each symptom (Scale 0-3: not present, mild, moderate, severe).

Each symptom will be assigned a score of 0 if not present, 1 if mild, 2 if moderate and 3 if severe. These scores for each symptom will be added together to get the CCSSSS for each day. This highest score during the 28 days after randomisation will be the maximum severity score. Scores on Day 1 and Day 2 will be excluded from this calculation.

Estimand

Population: Household members who test positive for SARS CoV-2 on day 1 by PCR

Treatment: Initially randomised intervention to unfractionated intranasal heparin 1400u each nostril (as heparin solution 5,000u/ml, 140microL/actuation, TWO actuations each nostril) THREE times daily via a plastic nasal inhalator device or saline control and any subsequent deviations to the per protocol use of the intervention over 10 days

Outcome: Maximum severity score calculated as the highest daily score on the CCSSSS during the 28 days after randomisation

Summary measure: The mean difference between arms will be reported with 95% confidence interval Potential intercurrent events:

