Index case in the household not taking study drug. This is defined as compliance <90% Participant (this household member) not taking study drug. This is defined as compliance <90% Either participant (this household member) or index case stop treatment due to adverse event Participant received an anti-viral

Strategy for handling intercurrent event:

All intercurrent events will be handled through the treatment policy strategy, which means that the intercurrent events will be ignored.

Treatment arms will be compared using mixed effects linear regression with maximum symptom severity as the outcome, adjusting for stratification factors (time from positive test to randomisation, whether the index case is a child < 5 years), participant age, inhaled steroid use at baseline, days since symptom onset at randomisation, whether there are children in the household and household size (referred to as the defined baseline covariate set), with household as random effect to take the clustering by household into account.

The mean difference between the treatment arms will be calculated in Stata as follows using a mixed effects GLM with random intercepts:

mixed outcome i.arm baseline_covariates || household:

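### Measure 4.3 is defined over Days 1-28 but calculated over Days 3-28 without a reason, and its model omits the participant's own severity at entry

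*SAP*

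**What the plan says.** Objective 4 in SAP Section 2.2 reads "To test the impact of intranasal heparin on peak severity of illness". Measure 4.3 under it is the maximum severity score of swab-positive participants "during the study period as recorded by daily symptom diary up to day 28". No days are left out there.

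Section 6.4 describes the daily score: 11 symptoms, each rated 0 to 3 and summed. It continues "This highest score during the 28 days after randomisation will be the maximum severity score", and the next sentence is "Scores on Day 1 and Day 2 will be excluded from this calculation". The Outcome line of the estimand that follows is "Maximum severity score calculated as the highest daily score on the CCSSSS during the 28 days after randomisation", without the exclusion.

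For the analysis, "Treatment arms will be compared using mixed effects linear regression with maximum symptom severity as the outcome". The model adjusts for the two stratification factors and "participant age, inhaled steroid use at baseline, days since symptom onset at randomisation, whether there are children in the household and household size", with a random intercept for household; the code is "mixed outcome i.arm baseline_covariates || household". Section 3.9 specifies that days since symptom onset is that of the index case. Section 2.5 ties time from positive test to the index case's test.

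**The concern.** One outcome has two definitions that give different values for the same participant, and each can be cited from Section 6.4. The definition that will be calculated does not match the stated objective. The population is already infected on Day 1, and index cases may enter up to 72 hours after their positive test (Section 2.3). Some participants will be at their worst on Day 1 or 2. For them the analysed number is a point on the way down, yet it would be reported in Table 16 as peak severity.

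The second part concerns the model. How ill a participant is at entry is likely to predict how ill they are from Day 3, but no measure of the participant's own entry severity is included. For a contact who is already positive on Day 1, the two timing covariates describe another person's illness. At stake are the width of the confidence interval and whether a chance difference in entry severity between the arms is adjusted for.

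**Working it through.** The SAP gives no standard deviation, effect size or power for Measure 4.3, so there is no figure to reproduce. Its only power calculation (Section 2.6) concerns the primary outcome.

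**1. The windows, side by side**

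| Place | Days used |
|---|---|
| Section 2.2, Measure 4.3 | up to Day 28, no exclusion |
| Section 6.4, definition sentence | 28 days after randomisation |
| Section 6.4, sentence after it | Days 1 and 2 removed: 28 - 2 = 26 days |
| Section 6.4, estimand Outcome line | 28 days after randomisation, no exclusion |
| Table 16 | labelled peak severity and maximum score, no window |

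**2. Effect on one participant (invented scores).** The scale runs from 0 to 11 x 3 = 33. With totals of 14, 15, 9, 7 on Days 1-4 and lower afterwards, the maximum over Days 1-28 is 15 and over Days 3-28 is 9.

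**3. Is a reason given?** Section 4.4 also drops Days 1 and 2, and explains why: the time of the first dose is unknown, so expected dose counts cannot be worked out. That concerns compliance. Measure 3.2 uses the same diary in the same population, keeps Day 1 as its reference and drops neither day.

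**4. What the model adjusts for.** Time from positive test and days since onset are both at index-case level. Age, steroid use, children in the household and household size do not measure severity. Day 1 symptom ratings exist, because Measure 3.2 judges improvement against them. Section 3.3 accepts as baseline only what was measured before study drug was dispensed.

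**5. Illustration of size; every parameter is assumed.** Daily scores were simulated for 268 households with two positive members each, a latent peak of 12 (SD 5) about 2.5 days after onset, and no treatment effect. Fits were by ordinary least squares with the index case's onset as covariate and no household effect.

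| Index onset before entry; mean lag of contact | Highest score on Day 1-2 | Mean maximum, Days 1-28 / 3-28 | Variance of Day 3-28 maximum explained by own time since onset | SE of arm difference without / with Day 1 score |
|---|---|---|---|---|
| 0-2 days; 1 day | 28% | 11.4 / 10.6 | 2% | 0.387 / 0.382 (1% lower) |
| 0-4 days; 1 day | 50% | 11.0 / 9.4 | 11% | 0.365 / 0.348 (5% lower) |
| 2-5 days; 1 day | 75% | 10.1 / 7.7 | 14% | 0.323 / 0.274 (15% lower) |
| 0-4 days; 3 days | 41% | 11.1 / 9.8 | 7% | 0.380 / 0.377 (1% lower) |

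The estimated arm difference centred on 0 with and without the Day 1 score. When scores in the active arm were assumed to be 20% lower from Day 2, the first three scenarios gave differences of -1.9, -1.4 and -0.6 over Days 1-28, and -2.0, -1.8 and -1.4 over Days 3-28. The two windows thus estimate different quantities.

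**6. The general formula.** If r is the partial correlation of the Day 1 score with the later maximum, given the covariates already in the model, the residual variance is multiplied by 1 - r². Assumed values of r = 0.3, 0.5, 0.7 give 0.91, 0.75, 0.51. The interval width is then multiplied by 0.954, 0.866, 0.714, that is, 5%, 13% or 29% narrower. The SAP does not tell us r.

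**The case against.** **The calculation is not really in doubt.** The exclusion comes straight after the definition, so a careful analyst would compute Days 3-28, and the Outcome line could be read as an incomplete restatement. This is fair as a prediction of what will be programmed. But the estimand is where the target is fixed, and it states another window, as does Section 2.2.

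**Leaving out the earliest days is defensible.** Treatment cannot change a score recorded before the first dose, and early scores dilute the contrast; the 20% scenarios above show this. This stands, so a Day 3-28 window can be a sound choice. The SAP does not give this reason, though, and the point about pre-dose scores does not by itself cover Day 2. Nor does it make a Day 3-28 maximum an overall peak.

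**The Day 1 score may not be a clean baseline.** The SAP does not say that the Day 1 diary precedes the first dose, and Section 4.4 says the time of day of starting is not recorded. This stands and limits the covariate to scores recorded before dispensing.

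**The model is valid without it.** This is also true. The covariate improves precision; it does not correct an error.

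A reader might infer that the analysed score is driven mainly by stage of illness at entry, or that the arm comparison is biased. The documents support neither. They hold no data on stage, they already adjust for two index-level timing variables, and randomisation balances stage in expectation.

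**Conclusion.** The mismatch of windows is plain on the page and needs no assumption. The analysed value is a Day 3-28 maximum, the stated estimand is a 28-day maximum, and no reason is given. The two differ for every participant whose highest score falls only on Day 1 or 2. The SAP does not allow that share to be estimated; 28% to 75% in the illustration follows from assumed illness curves.

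Omitting the participant's own entry severity costs precision and leaves chance imbalance unadjusted, but does not bias the randomised comparison. The size of the gain from adding it cannot be derived from the SAP: both the 1% to 15% in the simulation and the 5% to 29% from the formula rest on assumed inputs.

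This is a secondary outcome. The primary analysis and the sample size are untouched, but the point should be settled before the data are analysed.

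**What to change.** - State one window in identical terms in Section 2.2, in both the calculation paragraph and the Outcome line of Section 6.4, and in Table 16 (which also numbers the measure 4.1).
- If Days 1 and 2 stay out, name the outcome *maximum CCSSSS from Day 3 to Day 28*, give the reason, and do not describe it as overall peak severity.
- Report the maximum including the excluded days as a sensitivity analysis.
- Add the participant's own Day 1 CCSSSS to the model where it was recorded before study drug was dispensed (Section 3.3). Otherwise use the baseline symptom data listed in Section 4.2.
- Limit this covariate to Measure 4.3. Measures 5.1.2 and 5.1.5 in Section 6.5 reuse the Measure 4.3 model and would otherwise inherit it.

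The cost is a few lines of SAP text, one covariate from data already collected, and one extra analysis. The downside is that a simple rule is needed for Day 1 scores that are missing or were recorded after dispensing.
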